#### **10.2.8 Top 3 Concerns VAS**

The Top 3 concerns VAS allows subjects and caregivers to identify their main three causes of concern, related to the subject's myotonic dystrophy, rather than these being pre-specified within a scale and then rating how these concerns have changed at specific time-points during the study.

Subjects, where possible, and caregivers will be asked to rate three causes for concern by drawing a vertical mark on a 10cm long visual analogue scale with anchors of "not at all severe" at the left end and "very severe" at the right end. The 3 concerns related to the subject's myotonic dystrophy will be chosen and rated at baseline. These 3 signs and symptoms will be rated again at Week █ and EOT using the same scales.

A copy of the Top 3 concerns VAS is included in Appendix E.

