### **11.5      Statistical Methods for Efficacy**

Analyses of efficacy will be based primarily on the FAS.

Changes in efficacy variables from the start of the [REDACTED] run-in [REDACTED] to baseline [REDACTED] for each subject will be summarised and will be considered as indicative of the effect of [REDACTED] of [REDACTED] treatment. Changes from baseline [REDACTED] to post-treatment visits will be summarised by treatment dose at each study visit.

Analyses of changes from baseline will be performed where applicable using repeated measures analysis of covariance (ANCOVA) models with study site (if more than one is used) and treatment dose as fixed effects, and baseline value as a covariate. Least square mean estimates will be produced by dose group by study visit and will be presented with 95% confidence intervals and two-sided p-values.

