**17.5 Appendix E: Subject and Caregiver Top 3 Concerns**

Study AMO-02-MD-2-001	Site no.  /  / 	
Subject no.  /  / 		
Caregiver Top Three Concerns Baseline		
Date of assessment  dd /  mmm /  yyyy		
Please rate the three causes for concern associated with your relative and their myotonic dystrophy that you would most like to see change during treatment. You can select any sign or symptom.		
Your Concerns		
Concern number 1		
The sign or symptom causing concern is:		
How severe is the sign or symptom? Place a vertical mark on the line below to indicate how bad you think the sign or symptom has been in the past week, including today.		
 Completely Absent —————  Very Severe		
Concern number 2		
The sign or symptom causing concern is:		
How severe is the sign or symptom? Place a vertical mark on the line below to indicate how bad you think the sign or symptom has been in the past week, including today.		
 Completely Absent —————  Very Severe		
Concern number 3		
The sign or symptom causing concern is:		
How severe is the sign or symptom? Place a vertical mark on the line below to indicate how bad you think the sign or symptom has been in the past week, including today.		
 Completely Absent —————  Very Severe		

Study AMO-02-MD-2-001	Site no.   	
Subject no.   		
Subject Top Three Concerns Baseline		
Date of assessment  dd  mmm  yyyy		
Please rate the three causes for concern associated with your myotonic dystrophy that you would most like to see change during treatment. You can select any sign or symptom.		
Your Concerns		
Concern number 1		
The sign or symptom causing concern is:		
How severe is the sign or symptom? Place a vertical mark on the line below to indicate how bad you think the sign or symptom has been in the past week, including today.		
 Completely Absent  Very Severe		
Concern number 2		
The sign or symptom causing concern is:		

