How severe is the sign or symptom? Place a vertical mark on the line below to indicate how bad you think the sign or symptom has been in the past week, including today.		
 Completely Absent  Very Severe		
Concern number 3		
The sign or symptom causing concern is:		
How severe is the sign or symptom? Place a vertical mark on the line below to indicate how bad you think the sign or symptom has been in the past week, including today.		
 Completely Absent  Very Severe		

Study AMO-02-MD-2-001	Site no.  /  / 	
Subject no.  /  / 		
Subject Top Three Concerns Follow-Up		
Date of assessment  dd /  mmm /  yyyy		
At baseline, you rated the three causes for concern, related to your myotonic dystrophy that you most liked to see change during treatment. You selected the following signs or symptoms.		
Your Concerns		
Concern number 1		
The sign or symptom causing concern was:		
How severe is the sign or symptom? Place a vertical mark on the line below to indicate how bad you think the sign or symptom has been over the past week, including today.		
		
Concern number 2		
The sign or symptom causing concern was:		
How severe is the sign or symptom? Place a vertical mark on the line below to indicate how bad you think the sign or symptom has been over the past week, including today.		
		
Concern number 3		
The sign or symptom causing concern was:		
How severe is the sign or symptom? Place a vertical mark on the line below to indicate how bad you think the sign or symptom has been over the past week, including today.		
		

17.6 **Appendix F: Clinician-completed Domain Specific Causes for Concern:  
Myotonic Dystrophy (VAS)**

Study AMO-02-MD-2-001	Site no. 	
	Subject no. 	

### Clinician Domain-Specific Causes for Concern: Myotonic Dystrophy - Page 1 of 5

Date of assessment

dd       mmm       yyyy

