3.1.6 Scatterplots of Visit [] Data for Selected Efficacy Endpoints

Scatterplots will be presented indicating observed values at [] for each subject on selected endpoints. Subject number will be presented on the x-axis with the respective [] observed value on the y-axis. Subtitles, labels and footnotes will be adapted from the respective by subject line plots planned in this SAP. Where the endpoint is presented for different categories (e.g. preferred/fastest speed or dominant/non-dominant hand), each category will be displayed on a separate page. The endpoints to be presented will be:

- Time to complete 10m walk test (repeated for preferred and fastest speed)
- Handgrip Myometry (Grip strength and Relaxation time, repeated for the dominant hand and non-dominant hand)
- Pulmonary Function Test (FVC)
- Nine Hole Peg Test (dominant arm)
- Clinician-completed domain specific causes for concern VAS (repeated for total and domain specific VAS scores)
- Caregiver Top 3 Concerns Total VAS
- Peabody Picture Vocabulary Test (age based standard score)

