5.1.2.3 Top 3 Concerns Visual Analogue Scale (VAS)

The top 3 caregiver and subject concerns recorded for each subject will be mapped to the clinician-completed domain specific causes for concern.

A MMRM model will be fitted to the change from baseline to weeks [redacted] and [redacted] in the top 3 concerns VAS total score (derived as the total of the VAS scores for the three concerns) separately for the caregiver and subject. The model will be fitted and results presented as described in section 5.1.1.1.

The observed top 3 concerns VAS total score and corresponding change from baseline will be summarised over time separately for caregiver and subject. In addition, the above VAS scores at [redacted] and [redacted] and the change from [redacted] to [redacted] will be summarised. The observed top 3 concerns VAS total score will also be presented over time ([redacted] and [redacted]) using by subject line plots by dose group, separately for the caregiver and subject. In addition, line plots will present the adjusted LS mean changes from baseline and SEs over time, as estimated by the MMRM model, by dose group for the top 3 concerns VAS total score separately for the caregiver and subject. Raw mean changes from [redacted] to [redacted] will be presented on the same plot.

The top 3 concerns data, including the mapped domains and VAS scores will be listed. The listing will include change from baseline for the individual concerns VAS scores as well as the total VAS scores for each subject or caregiver.

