- Figure 14.2.3.1_AH1a Bar Chart of Pulmonary Function Test over Time – Mean Value +/- Standard Deviation
- Figure 14.2.3.1_AH1b Scatter Plot of Pulmonary Function Test at Week █
- Figure 14.2.5.1_AH1a Bar Chart of Time Taken (Seconds) to Complete the Nine Hole Peg Test over Time – Mean Value +/- Standard Deviation
- Figure 14.2.5.1_AH1b Scatter Plot of Time Taken (Seconds) to Complete the Nine Hole Peg Test at Week █
- Figure 14.2.6.1_AH1a Bar Chart of Clinical Global Impression over Time – Mean Score +/- Standard Deviation
- Figure 14.2.6.1_AH1b Bar Chart of Percentage of Subjects with Improvement at Baseline (End of █) and End of Treatment - Clinical Global Impression

Figure 14.2.7.1_AH1a Plot of Change from Week █ to Week █ in Clinician-completed Domain Specific Causes for Concern VAS: Myotonic Dystrophy

Figure 14.2.7.1_AH1b Plot of Change from Baseline to End of Treatment in Clinician-completed Domain Specific Causes for Concern VAS: Myotonic Dystrophy

Figure 14.2.7.1_AH1c Scatter Plot of Clinician-completed Domain Specific Causes for Concern VAS: Myotonic Dystrophy at Week █

Figure 14.2.9.1_AH1a Plot of Change from Week █ to Week █ in Caregiver Top Three Concerns VAS Total Score (cm)

Figure 14.2.9.1_AH1b Plot of Change from Baseline to End of Treatment in Caregiver Top Three Concerns VAS Total Score (cm)

Figure 14.2.9.1_AH1c Scatter Plot of Caregiver Top Three Concerns VAS Total Score (cm) at Week █

Figure 14.2.10.1_AH1a Bar Chart of OSU Global Improvement Scale for Autism over Time – Mean Score +/- Standard Deviation

Figure 14.2.10.1_AH1b Bar Chart of Percentage of Subjects with Improvement at Baseline (End of █) and End of Treatment – OSU Global Improvement Scale for Autism

Figure 14.2.11.1_AH1a Bar Chart of Peabody Picture Vocabulary Test over Time – Mean Value +/- Standard Deviation

Figure 14.2.11.1_AH1b Scatter Plot of Peabody Picture Vocabulary Test at Week -2

Figure 14.2.12.1_AH1a Bar Chart of DXA Scan (Body Composition - Lean Muscle Mass) over Time – Mean Value +/- Standard Deviation

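### The protocol has the Top 3 Concerns chosen and first rated at baseline, while the SAP appears to analyse an earlier rating; if the protocol is followed, this endpoint has no placebo-period reference

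*Protocol*

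**What the plan says.** **Protocol.** Section 10.2.8 states "The 3 concerns related to the subject's myotonic dystrophy will be chosen and rated at baseline" and continues "These 3 signs and symptoms will be rated again at Week █ and EOT using the same scales". No run-in rating is mentioned. Appendix E holds a form headed "Caregiver Top Three Concerns Baseline", a matching baseline form for the subject, and a follow-up form that opens "At baseline, you rated the three causes for concern, related to your myotonic dystrophy". The baseline forms ask for the concerns the rater most wants to see change, and allow any sign or symptom. Section 11.5 adds a general instruction, beginning "Changes in efficacy variables from the start of the", that run-in-to-baseline changes in efficacy variables be summarised as an indication of the run-in effect.

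**SAP.** Section 5.1.2.3 sets out the main model, separately for caregiver and subject: "A MMRM model will be fitted to the change from baseline to weeks" (week numbers redacted). It then adds a summary of scores at a second pair of visits and the change between them, and plots that raw mean change beside the model estimates. Section 3.1.1 applies comparisons over two intervals to the endpoints of 5.1.2.3. Section 3.1.5 plots two intervals for the caregiver total. Section 3.1.6 lists "Caregiver Top 3 Concerns Total VAS" among endpoints to be plotted at one redacted visit. Section 2.5 declares no departure from the protocol on this endpoint.

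**The concern.** The trial has no concurrent placebo arm, so the run-in is the only period against which on-drug change can be set. For the Top 3 Concerns, the protocol and the SAP seem to differ on whether a run-in value is collected. Either the protocol and forms omit a rating that was intended, or the SAP plans outputs from scores that nobody was told to collect.

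The choice visit matters more here than for a fixed scale. The rater picks the items, and if the pick is influenced by how bad they seem that week, the first score is high partly by selection and tends to fall at the next rating without any drug effect. If choice and first rating both happen at baseline, that fall is counted as change on tideglusib. Both the caregiver and the subject totals are modelled with p-values, and the caregiver total is one of nine outcomes in the Cohort 1 ad hoc tables.

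**Working it through.** **Step 1: is there a conflict?** Table 1 of the protocol is redacted, so the timing has to be read from the text.

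- *Baseline is not a loose word for Run-in.* The protocol names the two visits separately for the CGI (10.2.7), the OSU Autism CGI (10.2.11) and the Peabody test (10.2.12).
- *The second pair of visits in SAP 5.1.2.3.* The parallel sentence in SAP 5.1.1.1 is less redacted and identifies the pair as the start of the run-in and baseline.
- *The exemptions.* SAP 3.1.1 restricts only CGI-I and OSU CGI-I because they are not collected at the earlier visit, and treats DXA separately. Top 3 is not exempted.
- *The two plots.* In SAP Appendix 2, one caregiver Top 3 change plot runs from baseline to end of treatment. The other has its weeks redacted and is a separate interval.
- *The scatterplot visit.* SAP 3.1.6 uses one visit for all its endpoints, including the caregiver total and the Peabody test. Appendix 2 leaves one label visible: "Scatter Plot of Peabody Picture Vocabulary Test at Week -2". Active treatment starts at week 0, so this is before baseline.
- *Not obviously copied text.* The SAP omits the run-in pair for actigraphy and DXA but includes it for Top 3.

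Together these point to a Week -2 Top 3 score in the SAP, against none in the protocol.

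**Step 2: how large could the selection effect be?** The documents give no SD, reliability or power calculation, so there is no figure to reproduce and every input below is an assumption: a true severity SD of 2 cm between concerns (mean 5 cm), 8 candidate concerns, three chosen, an inert drug, and independent rating error with SD *e* on each occasion.

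Expected fall in the three-item total = S × e × c

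- S is the expected sum of the three largest of eight standard normals: 1.424 + 0.852 + 0.473 = 2.749.
- c is the correlation between whatever drives the choice and that day's rating error. If the choice follows the observed rating exactly, c = e / √(2² + e²).

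| e (cm) | c | Fall, choice wholly on that day's rating | Fall, choice score correlated 0.5 with that rating |
|---|---|---|---|
| 0.75 | 0.75/2.136 = 0.351 | 2.749 × 0.75 × 0.351 = 0.72 cm | 0.36 cm |
| 1.0 | 1/2.236 = 0.447 | 2.749 × 1.0 × 0.447 = 1.23 cm | 0.61 cm |
| 1.5 | 1.5/2.5 = 0.600 | 2.749 × 1.5 × 0.600 = 2.47 cm | 1.24 cm |

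If the choice depends only on stable severity, c = 0 and the fall is nil.

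Simulation with n = 8, scores limited to 0 to 10 cm and a one-sample test of change against zero (simpler than the planned model) gives the same falls. For choice wholly on that day's rating, p < 0.05 occurs in about 17%, 25% and 43% of trials. At correlation 0.5 the range is 7% to 13%. For stable severity it is 5%.

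With 5 candidate concerns, choice wholly on the rating gives 0.4 to 1.5 cm. With 17, the number of clinician domains, it gives 1.1 to 3.6 cm.

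**Step 3: what the choice visit changes.** If concerns are chosen and rated at Run-in and re-rated at Baseline, the whole selection-driven fall lands in the run-in. The simulated on-drug change is then 0.0 cm, with a 5% error rate in every setting.

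**The case against.** A reader might go further and infer that no run-in rating exists and that all regression to the mean falls on tideglusib. The documents do not support that as fact. Several parts of the SAP imply a Week -2 rating, and the schedule is redacted. If concerns were in fact chosen and rated at Run-in, the problem disappears.

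A reader might also take the 17% to 43% as the trial's false-positive rate. That too goes beyond the documents. The forms ask for what the rater most wants to change, not what is most severe, and they ask about the past week, which averages out some daily fluctuation. Choice on stable severity gives no bias at all. Adding unrelated preference noise to the choice (8 concerns, rating SD 1.0 cm) reduces the fall from 1.23 cm to 0.91 cm with noise SD 2 cm, and to 0.59 cm with noise SD 4 cm. The bias shrinks, but does not vanish while that day's severity plays some part.

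Protocol 11.5 is general and need not require a run-in value for every variable; DXA has none. This is a secondary endpoint in a trial whose primary objective is safety. Finally, the Cohort 1 outputs had already been reviewed when this SAP was written, so moving the choice visit could make the cohorts differ. All of this limits the claim about bias. None of it removes the disagreement over timing.

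**Conclusion.** The point holds as a conflict between documents with a conditional consequence. The protocol and its forms start this scale at baseline; the SAP appears, by inference from parallel text and one visible Week -2 label, to start it earlier.

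If the protocol wording is what sites follow, the planned run-in change cannot be computed for this endpoint, and any selection-driven fall is counted as on-drug change with no placebo-period value to reveal it. The size is unknown: nil under choice on stable severity, and about 0.4 to 2.5 cm of 30 cm under the 8-concern assumptions if that day's rating drives the choice in part or in full. Confidence in the conflict is good; confidence in any particular size of bias is low.

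**What to change.** - Amend Protocol 10.2.8 and Appendix E so that the three concerns are chosen and rated at Run-in, the same three are re-rated at Baseline, and then at the interim week and end of treatment.
- State in SAP 5.1.2.3 that the Baseline re-rating is the analysis baseline, and name the visits used for the run-in change.
- For any subject whose concerns were first chosen at Baseline, possibly all of Cohort 1, drop the run-in outputs for this endpoint. Footnote that the within-group change has no placebo-period reference and may include regression to the mean.

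**Cost.** One extra short form per rater at an existing visit, with matching edits to the protocol, forms and SAP. If Cohort 1 chose at Baseline and Cohort 2 chooses at Run-in, the cohorts will differ on this endpoint, and the report should say so. If a Run-in choice and rating were already in use, only the protocol and form wording needs correcting.

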### **10.2.9 Clinician completed Domain Specific Causes for Concern VAS: Myotonic Dystrophy**

The Clinician-completed Domain Specific Concerns is a Visual Analogue Scale (VAS) completed by the clinician that scores the severity of concerns in the following domains that are clinically relevant in myotonic dystrophy:

- Limitations with mobility or walking
- Problems with hands or arms
- Inability to do activities
- Fatigue
- Pain
- Gastrointestinal issues
- Problems with vision
- Communication difficulties
- Impaired sleep or daytime sleepiness
- Emotional issues
- Difficulty thinking
- Decreased satisfaction in social situations
- Decreased performance in social situations
- Myotonia
- Breathing difficulties
- Choking or swallowing issues
- Hearing difficulties

This list of domains is derived from the 17 subscales of the Myotonic Dystrophy Health Index (MDHI) (Heatwole *et al.*, 2014). The severity of the clinician's concern in each domain is scored by using a 10-cm visual analogue scale (VAS), with anchors of "not at all severe" at the left end and "very severe" at the right end. The clinician is asked to make a vertical line indicating his/her level of concern in each domain, using a time frame of the past week for reference. A score for each domain is determined by measuring the number of centimetres on the 10-cm VAS line from the anchor point on the left side of the line. A total VAS score for each subject is calculated as the sum of the scores for the 17 domains and is reported as both an absolute number and a percentage of the total possible line length (e.g. 170 cm).

The Clinician-completed Domain Specific Causes for Concern-VAS: Myotonic Dystrophy will be administered according the schedule of assessments.

A copy of the Clinician Domain Specific Causes for Concern VAS: Myotonic Dystrophy is included in Appendix F.

### **Assessments of cognitive functioning and associated neurodevelopmental symptoms**

#### **10.2.10 The OSU Autism Rating Scale—DSM-IV (OARS-4)**

The OARS-4 contains the autism signs and symptoms in the Diagnostic and Statistical Manual of Mental Disorders, 4th Edition (DSM—IV). These should be rated with the degree of impairment the subject experiences for the given symptom. The symptoms should be elicited in a semi-structured interview with the subject's primary caregiver. While scoring, the assessor should try to take both frequency/duration and degree of impairment into account as well as how much the item interferes with relationships, learning, and/or activities of daily living. Thus, rituals or preoccupations that severely interfere with most attempts to transition or that are present most of the time should be scored 2 or 3. Conversely, a ritual or preoccupation that is very mild, occupies little time, and interferes only mildly with daily events may be scored as 1.

The OARS-4 provides two summary scores (a) A weighted score based on severity of autism or autism spectrum symptoms derived from the clinical interview and (b) A symptom count, based on the same clinical interview

The OARS-4 should be completed according to the schedule of assessments, a copy of the scale is included in Appendix G.

#### **10.2.11 OSU Autism CGI scale**

The OSU Autism CGI scale contains separate subscales for symptom severity and for global improvement. These are rated in a similar way to the NIMH CGI Severity scale (see Clinical Global Impressions Severity and Improvement section in 10.2.6), but it is focused on autism spectrum symptoms. Symptoms frequently associated with autism spectrum—such as compulsions, hyperactivity, and self-injury should also be considered.

The CGI-I at Baseline (█) should be rated against the CGI-S at Run-in (█). The subsequent CGI-I ratings should be compared against the second CGI-S, done at Baseline (█).

The OSU Autism CGI scale provides 2 summary score (a) A global severity scale for autism, which takes autism spectrum and related symptoms (e.g., compulsions, problems transitioning, SIB) into account; and (b) A global improvement scale for autism.

The OSU Autism CGI scale (CGI-S and CGI-I) should be completed according to the schedule of assessments, a copy of the scale is included in Appendix G.

## **10.2.12 Peabody Picture Vocabulary Test**

The PPVT-4 scale is a norm-referenced instrument for measuring the receptive (hearing) vocabulary of children and adults. It contains training items and 228 test items, each consisting of four full-colour pictures as response options on a page. For each item, the examiner says a word, and the examinee responds by selecting the picture that best illustrates that word's meaning.

Each administration of the test produces a raw score as well as a standard score, derived from the number of responses attempted and the number of correct responses. The percent of correct responses is also reported.

The test will be performed at Run-in [REDACTED] Baseline [REDACTED] and End-of-Treatment [REDACTED] to compare scores prior and after single-blind placebo and single-blind tideglusib respectively.

10.2.13

Details on collection, handling, storage, processing and shipment of the [REDACTED] sample will be provided in a separate laboratory manual.

